4.7. Sexual maturation (Tanner Stage)

Sexual maturation of pediatric participants in long-term studies is assessed by using Tanner Stage.

Tanner stage is assessed in female participants ≥ 8 years of age and in male participants ≥ 9 years of age. For participants who enter the study below these ages sexual maturity assessments will start once they reach the ages of 8 or 9 years. Tanner stage assessment is stopped once full sexual maturation is reached.

Tanner stage data will be listed and summarized along with changes from baseline (Screening) over time.

Females of Childbearing Potential Status Change

Childbearing potential status assessed at screening will be listed with participant information, while changes in the status assessed for female participants at later timepoints will also be listed.

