#### **7.2.3.5 Tanner stage**

Per CHMP Paediatric addendum to the PAH guidelines [[EMA/CHMP/213972/2010](#)], the sexual maturation of pediatric participants in long-term studies is of particular importance. Therefore, the Tanner stage [refer to Section [14.5 Appendix 5](#)] is assessed at regular time points during the study.

Tanner stage is assessed in female participants  $\geq 8$  years of age and in male participants  $\geq 9$  years of age (i.e., examination is started once they are 8 and 9 years old, respectively). For participants who enter the study below these ages, sexual maturity assessments will start once they reach the ages of 8 or 9 years (for girls and boys, respectively). Tanner stage assessment is stopped once full sexual maturation is reached (if applicable before EOT). (Self-)Assessment of pubertal Tanner stage by parents or participants may be allowed by the study investigator. In this case, the investigator instructs and assists parents / participants on how this should be assessed at each time of the scheduled assessment.

The Tanner stages of puberty in girls are based on breast size and shape and pubic hair distribution. The Tanner stages of puberty in boys are based on the development of the genitalia and pubic hair distribution [[Blondell 1999](#), [Marshall 1969](#), [Marshall 1970](#)]. Actual age at milestone attainment may vary among individuals and among different study populations.

The site study personnel will record the Tanner stage in the eCRF.

For frequency of Tanner stage assessments, see schedule of assessments in [Table 4](#) and [Table 5](#).

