#### **10.3.5.7 Sexual maturation**

Absolute values and changes from baseline will be summarized over time up to EOT + 3 days, using descriptive statistics for continuous variables.

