7. STATISTICAL METHODS, CONVENTIONS FOR DISPLAYS AND DECIMAL PRECISION

Unless otherwise specified, all listings will be provided by center and participant number within each age cohort. They will be sorted then by assessment date as appropriate.

Descriptive summary statistics will be provided in the overall population, by age cohort and body weight group.

In summaries for categorical data all participants in the analysis set will be accounted for with tables displaying the number of participants with missing data. The number and percentage of participants in each category will be tabulated by visit as a shift table against baseline.

Summaries for continuous variables will include basic descriptive statistics: mean, median, first and third quartiles, standard deviation and range (minimum and maximum). Mean and median will be displayed as 1 decimal place more than the individual values. The standard deviations (SDs) will be displayed as 1 additional decimal place beyond that of the mean. If a count is 0, the percentage (0%) should not be displayed. The 0 count will be displayed, but the corresponding percentage should be omitted. If the corresponding denominator for the count is also 0, a hyphen (-) should be displayed rather than a 0 count or NA, and the corresponding percentage should be omitted.

- The participant percentages (%) presented in tables will be 1 decimal place unless the sample sizes for the percentages are small enough to warrant presenting as integers. The standard SAS rounding option will be used. For those percentages that rounds to 0.0, along with the count > 0, we will display < 0.1. For those percentages that would round to 100.0, where the count is less than the denominator, we will display > 99.9.
- All dates to be presented in Date9. format, along with time, wherever applicable.

Handling of Missing or Incomplete Date and Time Fields

Conventions for handling incomplete and missing dates are provided below. ‘Lower limit’ and ‘upper limit’ refer to the minimum or maximum, respectively, of a possible date. For example, if the day is missing, the lowest limit is the first day of the given month and the upper limit is the last day of the given month. If the day and month are missing, the lower limit refers to the 1st January of the given year and the upper limit to the 31st December of the given year.

Type of Date	Date is incomplete	Date is missing
Date of PAH diagnosis	Lower limit	No replacement

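### Tanner staging stops at full maturation and the last stage is not retained, so later summaries cover only children not yet recorded as mature; girls under 8 and boys under 9 at Screening have no baseline

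*SAP*

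**What the plan says.** **When staging starts.** SAP 4.7: "Tanner stage is assessed in female participants ≥ 8 years of age and in male participants ≥ 9 years of age". For younger entrants, Protocol 7.2.3.5 has: "For participants who enter the study below these ages, sexual maturity assessments will start once they reach the ages of 8 or 9 years".

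**When it stops.** SAP 4.7: "Tanner stage assessment is stopped once full sexual maturation is reached". Protocol 7.2.3.5 has the same rule and notes that this can happen before EOT.

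**How it is summarised.** SAP 4.7: "Tanner stage data will be listed and summarized along with changes from baseline (Screening) over time". It does not name the statistics. Protocol 10.3.5.7 does: "Absolute values and changes from baseline will be summarized over time up to EOT + 3 days, using descriptive statistics for continuous variables". The synopsis also asks for continuous statistics, and SAP section 7 includes the mean among them. For categorical data, SAP section 7 instead gives a shift table against baseline by visit, with missing counts shown.

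**Baseline.** SAP 2.4 requires a value before the first dose, so a first Tanner record taken on study cannot serve.

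**What is absent.** Neither document retains the final stage after staging stops, gives a substitute baseline for late starters, or separates these two groups from missing data. SAP section 5 mentions imputation only for exploratory efficacy.

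**The concern.** Change in Tanner stage up to EOT + 3 days is a named safety endpoint (Protocol 6.2), and Protocol 7.2.3.5 explains that maturation matters particularly in long-term paediatric studies. Treatment may run until 5 years after the last participant's first visit, so children will cross both age and maturity boundaries while on drug.

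The stop rule selects on the outcome: a child leaves the summary because the top stage was recorded. The set at each later visit is therefore less mature than the children being followed. With one arm, no comparator in the table would show that a low or falling mean stage comes from the rule and not from the drug. The start rule is a separate gap: some children can never contribute a change value, however long they are followed.

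**Working it through.** The plan states no figure for Tanner stage, so there is none to reproduce. The check has three parts.

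**1. Effect of the stop rule, by hand.** Assume 20 staged children, four at each of stages 1 to 5 at Screening, progressing 0.5 stage per year. The recorded stage is the whole part, capped at 5. A child is not assessed again after the first stage 5. "Retained" keeps stage 5 at later visits for all 20.

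| Year | Assessed | Mean stage, observed | Mean stage, retained | Mean change, observed | Mean change, retained |
|---|---|---|---|---|---|
| 0 | 20 | 3.0 | 3.0 | – | – |
| 1 | 16 | 2.5 | 3.0 | 0.0 | 0.0 |
| 2 | 16 | 3.5 | 3.8 | 1.0 | 0.8 |
| 3 | 12 | 3.0 | 3.8 | 1.0 | 0.8 |
| 4 | 12 | 4.0 | 4.4 | 2.0 | 1.4 |

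At year 1 no child has changed stage. The mean still falls from (1+2+3+4+5)/5 = 3.0 to (1+2+3+4)/4 = 2.5, because the four children mature at Screening are no longer assessed. It falls again from year 2 to year 3, when those who reached stage 5 at year 2 leave. At one stage per year, year 3 has 8 children assessed, with mean stage 4.5 against 4.8 and mean change 3.0 against 1.8.

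**2. Size in Cohort 1, by simulation.** All inputs are assumptions: ages uniform from 12 to 18; mean entry ages to stages 2, 3, 4 and 5 of 11.0, 12.3, 13.4 and 14.8 years; between-child SD 1.1 years; no drug effect; 400,000 children; visits as in Protocol Tables 4 and 5, with 28-day months.

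- About 53% are already at stage 5 at Screening, so about 47% are staged at Week 16. Observed mean stage goes from 4.17 at Screening to 3.51 at Week 16.
- At Month 16 about 30% are still assessed. Observed mean stage is 3.75, against 4.62 for the whole cohort and 4.19 for those below stage 5 at entry.
- Mean change, observed against all entrants below stage 5: 0.41 against 0.47 at Month 7; 0.94 against 0.96 at Month 16; 1.74 against 1.41 at Month 28. The largest understatement up to Month 16 is 0.08, at Month 10.

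The comparator matters for change. Children at stage 5 at entry have zero change by definition. Including them, the whole-cohort mean change at Month 16 is 4.62 − 4.17 = 0.45, and the observed 0.94 is higher. The hand example also includes them, which is why its observed change is never below the retained value.

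An SD of 0.8 or 1.4 gives the same pattern. Moving the entry ages by about 0.5 years moves the Month 16 assessed share between 23% and 39%.

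**3. Children with no baseline.** Cohort 3 (2 to under 6 years) lies wholly below the start age: about 20 of 60. In Cohort 2 (6 to under 12 years, about 20 children), assuming uniform ages:

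- all girls: 20 × (8 − 6)/6 = 6.7, total 26.7 of 60 (44%);
- all boys: 20 × (9 − 6)/6 = 10, total 30 of 60 (50%).

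With no age assumption the range is 20 to 40 of 60 (33% to 67%).

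**The case against.** **The SAP does not prescribe means.** This stands. SAP 4.7 says only that the data are summarised, and the continuous statistics come from the protocol, which leaves full analysis detail to the SAP. If Tanner stage is read as categorical, section 7 already gives a shift table with missing counts. SAP 2.3 leaves output detail to a data presentation plan that is not in the documents. But the SAP does not say which reading applies, and a shift table would still pool mature, not-yet-eligible and truly missing children.

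**The gaps would be visible.** Partly right. Data are listed and analyses are by age cohort, so Cohort 3 would plainly show no baseline. Listings do not, however, correct a misleading summary of mean stage.

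**The table would look like delayed puberty on drug.** A reader might infer this from the understated mean stage. The named endpoint is change, and that does not support the inference: among entrants below stage 5, change is almost unbiased at Month 16 and overstated by Month 28, the opposite of delay. With about 20 enrolled, about 8 are assessed at Month 10, so the 0.08 shortfall sits inside a standard error of about 0.18. At Month 28 about 4 of 20 remain.

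**Children who enter puberty on study contribute no change.** A reader might infer this too. It is true only of girls under 8 and boys under 9 at Screening. An older child who is still pre-pubertal at Screening has a baseline and contributes change.

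**Conclusion.** The point holds in a limited form. The stop rule, with no rule to retain the last stage, means each later visit summarises only children not yet recorded as mature. Under the protocol's continuous statistics, mean stage is understated and can appear to fall after Screening with no drug effect. Among entrants below full maturity, mean change is slightly understated early and overstated late. The direction for mean stage follows from the rule itself. The sizes depend on assumed stage-entry ages that are not in the documents, and on a single scale for both sexes, although Protocol 7.2.3.5 uses two components per sex.

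The missing baseline is certain for Cohort 3 and affects part of Cohort 2; the count of 27 to 30 of 60 assumes uniform ages in Cohort 2. The consequence is confined to one descriptive safety endpoint with no test. The primary PK objective is unaffected.

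**What to change.** In SAP 4.7:

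- **Retain the final stage.** Once full maturation is recorded, including at Screening, carry that stage to every later visit the child attends.
- **Name the summary type.** State that Tanner stage is categorical and apply the section 7 shift table by visit and sex, in place of the protocol's continuous statistics.
- **Label the structural gaps.** Show children not yet eligible by age, and children whose staging stopped at full maturity, separately from missing data. The second label explains why a retained value appears.
- **Late starters.** For children below the start age at entry, use the first on-study assessment as a reference value, labelled as such. Do not impute stage 1: the protocol schedules no staging below those ages, so that value would be unmeasured.

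The cost is SAP wording and minor programming, with no new assessments. The reference value for late starters is taken on treatment, so their changes should be shown apart from changes from a pre-dose baseline.

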4.8. Physical examination

All data will be listed.

5. EXPLORATORY EFFICACY ANALYSIS

All exploratory efficacy analyses will be carried out on the Safety Analysis Set, and be performed as follows:

- In the overall population.
- By age cohort.
- By body weight group

The main exploratory analysis will be based on observed data, with no imputation rules. Sensitivity analyses will be performed by imputing missing values as appropriate.

5.1. The Exploratory Endpoints

The exploratory endpoints are the following:

- Change from Baseline/Enrollment up to each time point of assessment in modified New York Heart Association / WHO FC.
- Change from baseline up to each time point of assessment in exercise capacity, as measured by the 6-minute walk distance (6MWD).

- Change from baseline in Panama FC up to each time point of assessment.
- Percent of baseline in plasma NT pro-BNP at each time point of assessment.
- Change from baseline up to each time point of assessment in Echo variables (imaging and Doppler evaluation):
 - Right ventricular systolic pressure.
 - Tricuspid annular plane systolic excursion.
 - Pulmonary artery acceleration time.
 - Left ventricular eccentricity index.
 - Right atrial area index (from apical 4 chamber view).
 - Tricuspid annular diameter (from apical 4 chamber view).
- Time to first of the following disease progression events occurring between first study drug dose and EOT + 7 days:
 - Death (all causes)
 - Atrial septostomy or Potts' anastomosis, or registration on lung transplant list
 - Hospitalization due to worsening PAH[§]
 - Clinical worsening* of PAH defined as: Need for, or initiation of new PAH-specific therapy[#] or i.v. diuretics or continuous oxygen use AND at least one of the following:
 - Worsening in WHO FC, or
 - New occurrence or worsening of syncope (in frequency or severity as per medical judgment), or
 - New occurrence or worsening of at least two PAH symptoms (i.e., shortness of breath/dyspnea, chest pain, cyanosis, dizziness/ near syncope, or fatigue), or
 - New occurrence or worsening of signs of right heart failure not responding to oral diuretics

[§]excluding hospitalizations that are elective, routine or clearly attributable to appearance/worsening of comorbidities (e.g., pneumonia).

*worsening from baseline.

[#]e.g., ERA, PDE-5 inhibitor, prostanoids, prostacyclin receptor (IP receptor) agonist, soluble guanylate cyclase stimulator.

5.2. Analysis of the Exploratory Efficacy Variables

5.2.1. Modified NYHA/WHO FC and Panama FC

At each time point, change from Baseline of assessment in modified NYHA/WHO FC and Panama FC will be classified as worsened (> baseline value), unchanged (= baseline value) or improved (< baseline value) and be summarized by age cohort and body weight group.

All data will be listed too by age cohort, site ID, participant ID and body weight group.

5.2.2. 6MWD

The change from baseline will be summarized at each time point of assessment up to the timepoint, using descriptive statistics for continuous variables. Two-sided 95% CIs of the mean and median will also be provided.

All exercise capacity data as measured by 6MWD test will be listed.

5.2.3. Plasma NT pro-BNP

The percent of baseline (defined as (NT pro-BNP value at the timepoint / NT pro-BNP at baseline [Day 1]) x 100) will be summarized at each time point of assessment and up to the timepoint with at least 10 participants in the age cohort, using descriptive statistics for continuous variables. The resulting mean and two-sided 95% CIs will be inversely transformed using the exponential function to provide the geometric mean and corresponding two-sided 95% CIs.

All data will be listed for each participant.

5.2.4. Echo/Doppler (assessed & transferred centrally)

The following Echo/Doppler variables, analyzed centrally, will be listed.

- Right ventricular systolic pressure (RVSP)
- Tricuspid annular plane systolic excursion (TAPSE)
- Pulmonary artery acceleration time)
- Left ventricular eccentricity index (LVEI)
- Right atrial area index (RAI)
- Tricuspid annular diameter

For each variable the change from baseline to each time point assessment will be summarized. Descriptive statistics for continuous variables will be displayed and the two-sided 95% CIs of the mean will also be provided.

5.2.5. Disease Progression/Clinical Worsening

Predefined signs and symptoms of PAH evaluated post baseline by the investigator to standardize the assessment of clinical worsening/disease progression and recorded in the eCRF will be listed.

In case of syncope or at least 2 new or worsening signs/symptoms the investigator must report disease progression in the eCRF and perform further exams to determine the cause.

Based on ‘Disease progression event summary’ the following time to event endpoint will be determined: time to disease progression/clinical worsening from first study drug dose up to EOT + 7 days.

All events (reasons) are considered:

- Death (all causes).

- Atrial septostomy or Potts' anastomosis, or registration on lung transplant list
- Hospitalization due to worsening PAH (excluding hospitalizations that are elective, routine or clearly attributable to appearance/worsening of comorbidities (e.g., pneumonia))
- Clinical worsening (from baseline) of PAH is defined as: need for, or the initiation of new PAH-specific therapy (e.g., ERA, PDE-5 inhibitor, prostanoids, prostacyclin receptor (IP receptor) agonist, soluble guanylate cyclase stimulator) or i.v. diuretics or continuous oxygen use AND at least one of the following:
 - Worsening in WHO FC, or
 - New occurrence or worsening of syncope (in frequency or severity as per medical judgment), or
 - New occurrence or worsening of at least two PAH symptoms (i.e., shortness of breath/dyspnea, chest pain, cyanosis, dizziness/ near syncope, or fatigue), or
 - New occurrence or worsening of signs of right heart failure not responding to oral diuretic

Deaths (all causes) not reported in “disease progression event summary” by the investigators will also be included in this analysis.

Event time is defined as the time elapsed from the first study drug administration to the day of the first occurrence of the event.

If the date of onset of the event is incomplete it is set to the lower limit, unless the lower limit is before the study treatment start date in which case it is set to the study treatment start date.

The number (and percentage) of participants reporting each type of event will be tabulated by age cohort, weight group and overall, for first event and for all events.

Participants who did not experience an event will have their event time censored at EOT + 7 days. The number of participants at risk, the number of participants censored and the number of participants with event will be displayed together with Kaplan Meier estimates.

This time to event endpoint will be also graphically presented as Kaplan Meier estimates with 2-sided 95% CIs at relevant time points (where the number of participants at risk is at least 10% of the total number of participants in the analysis set).

The type and date of disease progression event, as well as time to event, will be listed for all participants; as for the event type of “clinical worsening”, components of worsening will also be included in the listing, based on “clinical worsening of PAH”.

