AE resolution date	The earlier of the Upper limit and the end of study date	No replacement, considered ongoing at end of study
AE onset date	If the end date of the AE is not before the start of study drug, and if the study drug start falls in the range of possible dates, it is the study drug start date. In all the other cases, it is the lower limit	The earlier of the end date of the AE and the start of study drug
Concomitant medication start date	Lower limit	No replacement, the medication is considered to have started before the study
Concomitant medication end date	The earlier of the Upper limit and the end of treatment date	No replacement, considered ongoing at end of treatment
Death date	Last of the Lower limit and recorded study assessment dates	Last of the recorded study assessment dates

Anomalous information for a date will be handled using the following rules prior to using the imputations mentioned above:

If the day part of a date is non-numeric or has an invalid value, then day will be considered as missing. For example, if date = 44Nov2000 then, as it isn’t possible to have a 44th day of the month, the day will be considered missing.

If the month part of a date does not match that of the possible months, then it will be considered missing, and so will the accompanying day. For example, if date = 21ND99 then both day and month will be considered as missing.

If the year part of a date is non-numeric or has an invalid value, then the whole date will be considered as missing.

General Conventions:

- Study treatments start date is the first day of intake of study treatment. It is derived as the first 'Treatment start date' after sorting in chronological order all records. It coincides with Study Day 1.
- Study treatment end date (EOT) is the last day of intake of study treatment. It is derived as the last 'Treatment end date' after sorting in chronological order all records.
- Starting dose is the dose given on study treatment start date.

Study Day refers to the number of days elapsed since the day of study treatment start, plus 1 (i.e., Study Day 1 is the day of study treatment start). For dates prior to treatment start, it is the negative number of days elapsed between the date under consideration and the day of study treatment start. Therefore, the study day is always different from 0

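### SAP 5.2.5 and SAP 7 date an incompletely recorded death differently, and the 5.2.5 rule can place a death before a visit at which the child was alive

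*SAP*

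**What the plan says.** SAP 5.2.5 defines a composite time-to-event endpoint whose first component is death from any cause. It takes events from the investigator's disease progression summary and adds deaths found elsewhere: "Deaths (all causes) not reported in “disease progression event summary” by the investigators will also be included in this analysis". For partial dates it states "If the date of onset of the event is incomplete it is set to the lower limit", with one exception: "unless the lower limit is before the study treatment start date in which case it is set to the study treatment start date". On censoring it states "Participants who did not experience an event will have their event time censored at EOT + 7 days".

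SAP 7 defines the lower limit: "if the day is missing, the lowest limit is the first day of the given month", and "If the day and month are missing, the lower limit refers to the 1st January of the given year". Its table of date conventions has a separate row for the date of death. If that date is incomplete, the value used is "Last of the Lower limit and recorded study assessment dates". If it is missing altogether, the last recorded assessment date is used. The table has no row for non-fatal progression events.

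Neither section refers to the other or states precedence. Protocol 10.3.6.1 defines event time and censoring at EOT + 7 days but gives no rule for partial dates.

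**The concern.** One variable, the date of death, has two imputation rules within one SAP. The SAP 7 rule uses the fact that a child who attended an assessment was alive that day, so the imputed death cannot precede it. The 5.2.5 rule has no such safeguard, because its only floor is the start of treatment. As written, it can therefore put a death before a visit the child attended.

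At stake are the event time in the Kaplan-Meier estimates and the participant listing of event dates and times, where a death dated before a later visit would be visible. Two programmers following the SAP could also derive different times for the same child.

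**Working it through.** The plan gives no figure to reproduce. The check is date arithmetic on the two rules.

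**Inputs.** L is the lower limit (SAP 7). S is the treatment start. A is the last recorded assessment, on or after S. EOT is the last day of intake (SAP 7, General Conventions). The event window closes at EOT + 7 days (SAP 5.2.5).

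**Rules.**
- SAP 5.2.5: date = max(L, S)
- SAP 7 death row: date = max(L, A)
- Difference = max(0, A − max(L, S)), so the rules agree only when no assessment falls after max(L, S).

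**Illustrations.** All calendar dates are assumed. In the last four rows treatment starts on 1 March 2021.

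| Case | Death known as | Last assessment | SAP 5.2.5 | SAP 7 | Gap |
|---|---|---|---|---|---|
| Last dose 28 October, EOT visit on the last permitted day | November | 4 November | 1 November | 4 November | 3 days |
| Day missing, visit in the same month | June 2021 | 21 June | 1 June (92 days from start) | 21 June (112 days) | 20 days |
| Day and month missing | 2021 | 13 September | 1 March (0 days) | 13 September (196 days) | 196 days |
| Last visit in the previous month | June 2021 | 20 May | 1 June | 1 June | 0 |
| Last dose 10 June, contact on 25 June | June 2021 | 25 June | 1 June | 25 June | 24 days |

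In the first three rows and the last, 5.2.5 dates the death before a recorded assessment.

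**Can event status change?** The two rules disagree on status only if L ≤ EOT + 7 < A.
- Suppose the last contact is the EOT visit, which Protocol 7.1 and Table 5 require within 7 days of the last dose. Then A ≤ EOT + 7. If L ≤ EOT + 7, both rules place the death inside the window. If L > EOT + 7, both give L, outside it. Status is the same either way.
- The next scheduled contact is the EOS call, 30 days after the last dose plus up to 7 days (Table 5; Protocol 7.1 counts the 30 days from the EOT visit). A child alive at that call has completed the study (Protocol 8.1), and adverse events are recorded in the eCRF only up to EOS (Protocol 9.1.4). A later death is therefore unlikely to be in the data.
- That leaves an unscheduled contact after EOT + 7 and before the EOS call. The last row is such a case. EOT + 7 is 17 June, the EOS call falls between 10 and 17 July, and the contact on 25 June, 15 days after the last dose, is not scheduled. Under 5.2.5 the death on 1 June is an event. Under SAP 7 the death on 25 June is outside the window and the child is censored.

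**Population.** The analysis uses the Safety Analysis Set (SAP 5), planned at about 20 children per cohort and 60 overall (SAP 1.2).

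**The case against.** The strongest reply is that the sections can be read together. SAP 5.2.5 uses a term defined only in SAP 7. The SAP 7 table treats death as a date type of its own and has no row for progression events, so 5.2.5 may be meant to fill that gap for non-fatal events, where onset is the natural word. Applied first, the SAP 7 death row would complete the date before 5.2.5 came into play. This reading is sensible and may be what was intended. It is not stated: 5.2.5 uses the word event for the whole list, death comes first in that list, and the only exception concerns treatment start. One section is specific to the variable and the other to the endpoint, so precedence can be argued either way.

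It is also fair that partial death dates should be rare. A death is a serious adverse event reportable within 24 hours of the investigator's knowledge (Protocol 9.2.5), and deaths inside the window occur on treatment or within a week of the last dose. A date known only by year is very unlikely. This limits the size of the problem but does not remove the conflict.

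**Conclusion.** The SAP is wrong as written: two sections give different dates for the same death, and one of them can be an impossible date. Severity is low. The endpoint is exploratory and descriptive in a single-arm study, and the primary PK endpoint is untouched. The problem needs a partial death date together with an assessment after max(L, S).

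Four stronger readings are not supported:

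- **That the conflict generally changes which children count as events.** It ordinarily moves only the time of the event. A change of status needs the unscheduled contact described above.
- **That one death shifts a cohort estimate by 1/15 = 6.7%.** Fifteen is the target for evaluable PK profiles, not the size of the Safety Analysis Set. Even 1/20 = 5% is the Kaplan-Meier step only if nobody has yet been censored or had an event. Where both rules count the death, what changes is the time of the step, and its height only as far as the number at risk differs at the two dates.
- **That errors of 30 days (day missing) or 364 days (day and month missing; 365 in a leap year) are to be expected.** These are extreme bounds. They need the child to be assessed on the last possible day, which would itself fix the date of death.
- **That the lower-limit rule is also defective for non-fatal events.** SAP 7 has no competing row for them, so no conflict exists, and dating their onset at the lower limit is a legitimate conservative choice.

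**What to change.** Add one sentence to SAP 5.2.5: incomplete or missing dates of death follow the death-date row in SAP 7, and the lower-limit rule in this section applies to the non-fatal events only. Naming missing dates also settles a fully missing date of death, for which 5.2.5 has no rule and SAP 7 does. Leave the rule for non-fatal events as it is.

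The change uses the sponsor's own convention and needs no new data, no extra analysis and no protocol amendment. The cost is one line in the SAP and the matching line in the derivation specification.
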